3.6.1 Schedule of Assessments

3.6.1.1 Screening/Baseline

Screening for rollover subjects occurs simultaneously with baseline at the Week 12 or ET, if the trial is terminated, visit of Trial 331-14-213 (see [Table 3.6-1](#)). Rollover subjects entering Trial 331-201-00182 must sign the ICF for the active-treatment trial before any procedures specific to Trial 331-201-00182 can be performed. Subjects will retain the same subject identification (ID) number assigned in the double-blind, phase 3 Trial 331-14-213. Screening/baseline values will be derived from the Week 12 or ET visit of Trial 331-14-213 for the following assessments: CMAI, CGI-S, SAS, AIMS, BARS, Sheehan-STS, physical/neurological examination, waist circumference, vital signs, ECG, and clinical laboratory tests. The only additional procedures to be performed for rollover subjects at screening/baseline of the active-treatment trial are as follows:

- Inclusion/exclusion criteria for Trial 331-201-00182 will be reviewed to ensure the subject's eligibility.
- Medical history will be updated, if necessary.
- Concomitant medications will be reviewed to ensure that the subject is not receiving any prohibited medications.
- Brexpiprazole will be dispensed to the subject.
- AE recording will begin with the signing of the ICF for Trial 331-201-00182.
- The subject will take the first dose of the IMP the day after the baseline visit. The subject should take the IMP at approximately the same time each day, preferably in the morning, without regard to meals.

3.6.1.2 Weeks 1, 2, and 6

All subjects will be evaluated at Weeks 1 and 2. Visits are to occur within \pm 2 days of the target visit date. All required evaluations will be performed as described in the Schedule of Assessments ([Table 3.6-1](#)). The following should also be noted:

- The investigator must determine if there have been any changes to the prior assessment of the subject's capacity to provide informed consent. If changes have been made, refer to the instructions detailed in [Section 3.4.1.1](#).
- IMP accountability will be performed.
- The subject will start taking the IMP from the assigned blister card the day after the clinic visit. The subject should take the IMP at approximately the same time each day, preferably in the morning, without regard to meals.

Protocol 331-201-00182

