7.6.1 Adverse Events

All AEs will be coded by system organ class and Medical Dictionary for Regulatory Activities (MedDRA) preferred term. The incidence of the following events will be summarized descriptively:

- TEAEs
- TEAEs by severity
- TEAEs potentially causally related to the IMP (per investigator)

Protocol 331-201-00182

- TEAEs with an outcome of death
- Serious TEAEs
- TEAEs leading to discontinuation of the IMP

A TEAE is defined as an AE that starts after the first dose of IMP in the extension trial or an AE that is reported at baseline and increases in intensity or becomes serious or trial drug-related or results in death, discontinuation, interruption, or reduction of IMP.

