SAP 331-201-00182

List of Abbreviations and Definitions of Terms

Abbreviation	Definition
AAD	Agitation in Alzheimer's dementia
AE	Adverse event
AIMS	Abnormal Involuntary Movement Scale
ALT	Alanine aminotransferase
AST	Aspartate aminotransferase
BARS	Barnes Akathisia Rating Scale
BMI	Body mass index
CGI-S	Clinical Global Impression - Severity
CRF	Case Report Form
CMAI	Cohen-Mansfield Agitation Inventory
DBP	Diastolic blood pressure
ECG	Electrocardiogram
EPS	Extrapyramidal symptoms
ET	Early termination
FDA	(United States) Food and Drug Administration
HbA1c	Glycosylated hemoglobin
HDL	High density lipoprotein
IAF	Informed assent form
ICF	Informed consent form
ID	Identification
IMP	Investigational medicinal product
IRE	Immediately reportable event
LDL	Low density lipoprotein
LOCF	Last Observation Carried Forward
MedDRA	Medical Dictionary for Regulatory Activities
OPDC	Otsuka Pharmaceutical Development and Commercialization, Inc.
PE	Physical examination
QD	Once Daily
QTc	Corrected QT interval
QTcF	QT interval as corrected for heart rate by Fridericia's formula
SAE	Serious adverse event
SAS	Simpson Angus Scale
SAS®	Statistical Analysis System®
SAP	Statistical Analysis Plan
SCS	Summary of Clinical Safety
SOC	System Organ Class
TEAE	Treatment-emergent adverse event
ULN	Upper limit of normal

SAP 331-201-00182

1 Introduction

This statistical analysis plan (SAP) expands the statistical section of the protocol 331-201-00182 and documents in detail the statistical methodologies and data analysis algorithms and conventions to be applied to the analysis and reporting of the safety and tolerability data collected in the study. All amendments to the protocol have been taken into consideration in developing this SAP.

2 Study Objectives

Primary: To assess the long-term safety and tolerability of oral brexpiprazole as treatment in adult subjects with AAD.

3 Trial Details

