8.1 COVID-19 Related Supplementary Analyses

Summary statistics for mean and mean change from baseline in CMAI total score, by trial visit and at the last visit (i.e., Week 12/ET) and by visit type (face-to-face vs. remote) based on the Efficacy Sample will be provided by parent study treatment group for rollover subjects and overall.

9 Safety Analysis

The primary safety endpoint analysis is the frequency and severity of AEs in the open-label treatment phase (see [Section 9.1](#)). Other standard safety variables to be analyzed include clinical laboratory tests, vital signs, body weight, waist circumference, BMI, 12-lead electrocardiograms (ECGs), and physical examinations. In addition, data from the following safety scales will be evaluated: MMSE score, assessments of suicidality (eg, Sheehan-STS), and extrapyramidal symptoms (EPS; eg, the Simpson-Angus Scale, abnormal involuntary movement scale [AIMS], and Barnes Akathisia Rating Scale [BARS]).

Safety analyses will be conducted based on the Safety Sample, and summary statistics will be provided by parent study treatment group and overall, unless otherwise specified.

The long-term 24 weeks (6 months) safety analysis for subjects who received brexpiprazole in the parent trial 331-14-213 will be described in the SAP for the Summary of Clinical Safety (SCS) for Agitation in Alzheimer's dementia (AAD) and the results will be presented in the SCS.

Unless otherwise specified, in general, analysis of safety data will be performed on observed case and for last visit.

SAP 331-201-00182

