9.1 Adverse Events

All adverse events will be coded by System Organ Class (SOC) and Preferred Term (PT) according to the Medical Dictionary for Regulatory Activities (MedDRA). AEs that are sex-specific, eg, ovarian cancer, will have their incidence rates evaluated for the specific sex.

Treatment-emergent AEs (TEAEs) are defined as AEs with an onset date on or after the first dose of IMP. In more detail, TEAEs are all adverse events which started after start of IMP; or if the event was continuous from baseline and was worsening, serious, study drug related, or resulted in death, discontinuation, interruption or reduction of study therapy. Adverse events occurring up to 30 days after the last day of IMP will be included in the summary tables.

The incidence of the following events in the open-label treatment phase will be tabulated by treatment group and overall using the Safety Sample:

- a) Treatment-emergent AEs (TEAEs)
- b) TEAEs by severity
- c) TEAEs potentially causally related to the IMP
- d) TEAEs with an outcome of death
- e) Serious TEAEs
- f) TEAEs leading to discontinuation of the IMP

The above summaries (b), (e) and (f) will also be prepared for TEAEs potentially causally related to the IMP.

In addition, incidence of TEAE during the open-label treatment phase of at least 5% by SOC and PT will be provided.

Incidence of TEAEs by SOC and PT will be summarized for sex, race, age and region subgroups.

Extrapyramidal symptoms (EPS)-related AEs will be grouped into five categories.

1) Dystonic Events, which include blepharospasm, cervical spasm, clumsiness, dystonia, dystonic tremor, emprosthotonus, essential tremor, facial spasm, fumbling, gait inability, head titubation, intention tremor, Meige's syndrome, muscle contractions involuntary, muscle spasms, muscle spasticity, muscle tightness, muscle tone disorder, musculoskeletal stiffness, myotonia, nuchal rigidity, oculogyration, oesophageal spasm, opisthotonus, opisthotonus, oromandibular dystonia, oropharyngeal spasm, pharyngeal dystonia, pleurothotonus, risus

SAP 331-201-00182

sardonicus, spasmodic dysphonia, tongue spasm, torticollis, torticollis psychogenic, trismus, uvular spasm;

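### SAP 9.1 does not reproduce the protocol's TEAE rule: its first sentence excludes every baseline AE, and its second counts baseline AEs that were already serious or drug-related and did not change

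*SAP*

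**What the plan says.** Protocol 7.6.1 gives one rule with two limbs. The onset limb reads "A TEAE is defined as an AE that starts after the first dose of IMP in the extension trial". The baseline limb admits "an AE that is reported at baseline and increases in intensity or becomes serious or trial drug-related", and also a baseline AE that leads to death or to stopping, interrupting or reducing IMP.

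SAP 9.1 gives two sentences. The first is an onset rule with nothing about baseline events: "Treatment-emergent AEs (TEAEs) are defined as AEs with an onset date on or after the first dose of IMP". The second begins "In more detail, TEAEs are all adverse events which started after start of IMP" and adds a baseline limb: "or if the event was continuous from baseline and was worsening, serious, study drug related, or resulted in death", followed by discontinuation, interruption or reduction of treatment.

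The SAP's Introduction presents the document as an elaboration of the protocol, not a departure from it: "This statistical analysis plan (SAP) expands the statistical section of the protocol 331-201-00182". Nothing in the SAP explains the change of wording or restores the protocol's condition elsewhere. SAP Section 9 sets out what depends on the definition: "The primary safety endpoint analysis is the frequency and severity of AEs in the open-label treatment phase".

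**The concern.** For seriousness and relatedness, the protocol asks whether something changed (the AE *becomes* serious or related). The SAP's detailed sentence asks only whether a state held (the AE *was* serious or related). A programmer who follows the SAP would flag an old, unchanged serious or related AE as newly emergent. A programmer who follows the SAP's first sentence would drop baseline AEs that the protocol wants counted.

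The flag feeds all six TEAE tables in SAP 9.1, and the tables by severity, for serious events and for discontinuations are repeated for related TEAEs. Seriousness and relatedness, the two criteria affected, are therefore themselves reported results.

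**Working it through.** The plan states no figure here and no arithmetic applies, so the check sets the three rules side by side. The inputs are Protocol 7.6.1, SAP 9.1 first sentence (onset) and SAP 9.1 second sentence (detail). Each row is an AE that began before the first extension dose and is continuous from baseline. A listed outcome means death, or discontinuation, interruption or reduction of IMP.

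| AE continuous from baseline | Protocol 7.6.1 | SAP, first sentence | SAP, second sentence (literal) |
|---|---|---|---|
| 1. Already serious, unchanged, no listed outcome | not a TEAE | not a TEAE | TEAE |
| 2. Already drug-related, unchanged, no listed outcome | not a TEAE | not a TEAE | TEAE |
| 3. Becomes serious or drug-related | TEAE | not a TEAE | TEAE |
| 4. Increases in intensity | TEAE | not a TEAE | TEAE |
| 5. Has a listed outcome | TEAE | not a TEAE | TEAE |
| 6. Non-serious, unrelated, unchanged, no listed outcome | not a TEAE | not a TEAE | not a TEAE |

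**Reading the table.**

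- The first SAP sentence differs from the protocol in rows 3, 4 and 5.
- The second differs in rows 1 and 2. Neither sentence agrees with the protocol throughout, and the two SAP sentences disagree with each other in rows 1 to 5.
- In rows 4 and 5 the second sentence matches the protocol: *worsening* still requires a change, and the outcome criteria are the same in substance.

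**Direction.** For these AEs the second sentence counts everything the protocol counts (rows 3 to 5) and also rows 1 and 2. Its TEAE, serious and related counts are therefore equal to or higher than the protocol's, never lower.

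**Size.** A row 1 or row 2 event must be in the extension AE data before the first dose. Protocol 3.6.1.1 says "AE recording will begin with the signing of the ICF for Trial 331-201-00182" and puts the first dose on the day after the baseline visit. If only newly arising AEs are recorded, the pre-dose window is about one day. The documents give no count of AEs ongoing at rollover, so no number of affected subjects can be computed.

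**Onset on the first-dose day.** The SAP's first sentence includes it (on or after); its second sentence and the protocol say after. An AE dated to that day, with its order relative to the dose unknown, is in under the first sentence and undetermined under the other two.

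**The case against.** The strongest reply is that this is loose drafting. The SAP's list has the same items in the same order as the protocol's and reads naturally as a shortened version of it. The over-count needs a literal reading, and the SAP's first sentence, the one phrased as the definition, would exclude rows 1 and 2. In addition, the documents point to few or no affected events, and the trial is descriptive.

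Much of this stands, and it is why the point is minor. It does not remove the conflict. If the first sentence governs, the SAP omits baseline AEs that the protocol counts. If the second governs, as its lead-in suggests, the text as written admits rows 1 and 2.

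A reader might infer four stronger things that the documents do not support:

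- *The SAP drops the change requirement altogether.* It does so only for seriousness and relatedness.
- *The detailed sentence also under-counts, because it says continuous from baseline where the protocol says reported at baseline.* That needs an intermittent AE kept as one record from before the first dose. No section describes such a recording convention, and a recurrence recorded as a new AE after the first dose counts under both rules.
- *The first dose of IMP might mean the parent trial's first dose.* SAP 9.1 tabulates the open-label phase, and SAP 9.9 and 10.1 count from the first open-label dose, so context settles this.
- *Former brexpiprazole subjects will show inflated related counts, because they arrive with drug-related AEs still ongoing.* This is possible only if AEs ongoing from Trial 331-14-213 enter the extension AE dataset. No section says that they do, and AEs are not among the values that Protocol 3.6.1.1 takes from the parent trial's last visit.

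**Conclusion.** The point holds as a conflict of wording between the SAP and the protocol on the definition behind the primary analysis. Neither SAP sentence gives the protocol's classification. Under the detailed sentence read literally, the error for AEs continuous from baseline is one-sided, towards more TEAEs, serious TEAEs and related TEAEs.

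The amount is unknown and may be zero. It depends on how many AEs already serious or already drug-related are recorded before the first extension dose and then neither change nor have a listed outcome. The conclusion about wording assumes only that the SAP is programmed as written. No hypothesis test, sample size or power statement depends on it. Severity: minor.

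**What to change.** Replace both SAP sentences with one definition that uses the protocol's verbs. The onset limb should be the protocol's own, tied to the first dose of IMP in Trial 331-201-00182. The baseline limb should cover an AE reported at baseline that increases in intensity, becomes serious, becomes drug-related, or leads to death or to stopping, interrupting or reducing IMP. State that change is judged against the AE's status at the extension baseline.

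Set one convention for onset on the first-dose day and use it in both documents.

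The cost is a change of wording and of one derivation, with no new data collection. Compared with literal programming of the detailed sentence, counts of baseline AEs may fall slightly or not change. If the first sentence had been programmed instead, baseline AEs that the protocol counts would be added back.

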9.2 Clinical Laboratory Tests

9.2.1 Change from Baseline in Lab Tests

Summary statistics for mean and mean change from baseline in the routine clinical laboratory measurements, prolactin concentrations, coagulation parameters (prothrombin time, activated partial thromboplastin time, and international normalized ratio), HbA1c, and thyroid-stimulating hormone will be provided by parent study treatment and by visit.

SAP 331-201-00182

9.2.2 Potentially Clinically Relevant Values

[figure not shown]
In addition, the incidence of treatment-emergent PCR values identified using prospectively defined criteria for laboratory tests will be summarized by parent study treatment group. A listing of PCRs by subject and by test will be provided.

9.2.3 Potentially Liver Injury Related Laboratory Test

Total bilirubin level will be checked for any subjects with increased alanine transaminase (ALT) or aspartate transaminase (AST) levels greater or equal to three times the upper normal limits (or baseline).

Liver injury related laboratory test results will be summarized for subjects who met following criteria for Safety Sample during the open-label treatment period. The corresponding listing will be provided as well.

- AST or ALT $\geq 3 \times$ upper limit of normal (ULN) and
- T_Bili $\geq 2 \times$ ULN

SAP 331-201-00182

9.3 Physical and Neurological Examination and Vital Signs

Physical and neurological examination findings will be listed by subject.

Summary statistics for change from baseline in vital signs, body weight, BMI, and waist circumference will be provided by parent study treatment group.

In addition, the incidence of treatment-emergent PCR values identified using prospectively defined criteria for vital signs and body weight will be summarized by parent study treatment group. Listing of PCRs by subject and by test will be provided.

9.4 12-Lead ECG

Summary statistics for change from baseline in ECG parameters will be provided by parent study treatment group and by visit.

In addition, the incidence of treatment-emergent PCR values identified using prospectively defined criteria for ECG will be summarized by parent study treatment group. Listing of PCRs by subject and by test will be provided.

For the analysis of QT and QTc, data from three consecutive complexes (representing three consecutive heart beats) will be measured to determine average values. The following QT corrections will be used for reporting purposes in the clinical study report:

- QTcB is the length of the QT interval corrected for heart rate by the Bazett formula: $QTcB=QT/(RR)^{0.5}$
- QTcF is the length of the QT interval corrected for heart rate by the Fridericia formula: $QTcF=QT/(RR)^{0.33}$
- QTcN is the length of the QT interval corrected for heart rate by the FDA Neuropharm Division formula: $QTcN = QT/(RR)^{0.37}$

Categorical changes in ECG parameters during the open-label treatment period will be summarized based on the criteria in [Table 9.4-1](#).

SAP 331-201-00182

Table 9.4-1 Categorical Change Criteria in QT/QTc Parameters

Classification	Category	Criteria
QT	New onset (≥ 450 msec for men or ≥ 470 msec for women)	New onset in QT means a subject who attains a cut off value during treatment period but not at baseline.
QTc ^a	New onset (≥ 450 msec for men or ≥ 470 msec for women)	New onset in QTc means a subject who attains a cut-off value during treatment period but not at baseline.
	New onset (≥ 450 msec for men or ≥ 470 msec for women) and $> 10\%$ increase	New onset and $> 10\%$ increase in QTc means a subject who attains a cut off value and $> 10\%$ increase during treatment period but not at baseline
	New onset (> 500 msec)	New onset (> 500 msec) in QTc means a subject who attains a value > 500 msec during treatment period but not at baseline.
	Increase 30 - 60 msec	Increase from baseline value > 30 and ≤ 60 msec in QTc
	Increase > 60 msec	Increase from baseline value > 60 msec in QTc

^a QTc categorical change criteria apply to QTcB, QTcF and QTcN.

9.5 Simpson-Angus Scale, Abnormal Involuntary Movement Scale, and Barnes Akathisia Rating Scale

The mean change from baseline in SAS, AIMS, and BARS scales for trial visits during the open-label treatment phase using the Safety Sample will be summarized by descriptive statistics. In addition, incidence of BARS Global Clinical Assessment of Akathisia during the open-label treatment phase by severity category will be provided. Descriptive statistics will be summarized at each visit using the OC data set and at the last visit (Week 12/ET) using the LOCF data set.

9.6 Mini-Mental State Examination

The mean changes from baseline in MMSE for trial visits during the open-label treatment phase will be summarized by descriptive statistics. Descriptive statistics will be summarized at each visit using the OC data set and at the last visit (Week 12/ET) using the LOCF data set.

9.7 Suicidality Data

The mean changes from baseline in Sheehan-STS individual item scores, suicidal ideation subscale score, suicidal behavior subscale score, or total score for trial visits during the open-label treatment phase using the Safety Sample will be summarized by descriptive statistics. Descriptive statistics will be summarized at each visit using the OC data set and at the last

SAP 331-201-00182

visit (Week 12/ET) using the LOCF data set. Incidence of treatment emergent suicidal ideation, suicidal behavior will be summarized by treatment, and overall.

9.8 Concomitant Medications

Number and proportion of subjects taking concomitant medications prior to IMP, during the open-label treatment period, and after IMP are tabulated by drug classification using the World Health Organization drug dictionary.

9.9 Extent of Exposure

The start date of open-label IMP will be the first day of open-label IMP dosing. The number and percentage of subjects who receive open-label IMP will be presented by week and by parent study treatment group. Each dosing week will be based on the actual week; i.e., Day 1 to 7 in Week 1, Day 8 to 14 in Week 2, etc. This summary will be performed on the Safety Sample.

The number and percentage of completers will be presented by week and by parent study treatment group.

The mean daily dosage will be summarized by week and parent study treatment group using descriptive statistics. The mean daily dosage per subject per week will be determined for each week of the trial. This will be calculated by dividing the sum of individual total doses by the number of days in the week interval. The summary will contain for each parent study treatment group the number of subjects receiving open-label IMP, and the mean and range of the mean daily dose for each week.

10 Conventions

10.1 Study Visit Windows

Trial visit windows will be used to map visits using trial day intervals. This visit window convention applies to tables and listings for all efficacy and safety scales (CMAI, CGI-S, SAS, AIMS, BARS, MMSE and Sheehan-STS). This derived trial window variable will be named as WEEK and will be footnoted. In listings it will be listed along with the case report form (CRF) trial visit.

Table 10.1-1 below shows classifications for trial day intervals in the open-label treatment period. The variable “target day” is defined using the number of days since the start of open-label brexpiprazole dosing. The first day of open-label brexpiprazole dosing is defined as “Day 1”. If more than one observation falls within a particular trial day interval, then the last observation within that interval is used. Evaluations occurring more than 7 days after the last

SAP 331-201-00182

open-label brexpiprazole dosing date will not be mapped into study visit windows and will be excluded from the analysis.

Table 10.1-1 Mapping of the Analysis Visit for the Open-label Treatment Period		
Analysis Visit	Target Study Day ^a per Protocol	Study Day Interval^a (endpoint inclusive)
Day 1	1	1
Week 1	7	2 to 10
Week 2	14	11 to 28
Week 6	42	29 to 63
Week 12	84	64 to 91

^a Relative to the first day of IMP in the open-label treatment period.

^b Evaluations occurring more than seven days after the last dosing date of IMP in the open-label treatment period will be excluded from the efficacy analyses.

The preceding algorithm ensures that all observations collected at an ET visit or any other unscheduled visit will be mapped to an analysis visit. In instances where multiple observations (of same parameter on the same subject) fall into one study day interval, all values of the multiple observations in the study interval will be included for listings, but only the last observation will be used for the by-visit analysis or summary.

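### SAP 10.1 gives no single rule for scale values taken more than 7 days after the last dose and has no window after Day 91; separately, SAP 7.1 defines baseline too narrowly (low severity)

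*SAP*

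**What the plan says.** **Windows.** SAP 10.1 states its scope first: "This visit window convention applies to tables and listings for all efficacy and safety scales". The list that follows names SAS, AIMS, BARS, MMSE and Sheehan-STS as well as CMAI and CGI-S. Three statements then deal with late or off-schedule values:

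- Body text: evaluations over 7 days past the last "open-label brexpiprazole dosing date will not be mapped into study visit windows and will be excluded from the analysis".
- Table 10.1-1, footnote b: evaluations "more than seven days after the last dosing date of IMP in the open-label treatment period will be excluded from the efficacy analyses".
- Closing paragraph: "The preceding algorithm ensures that all observations collected at an ET visit or any other unscheduled visit will be mapped to an analysis visit".

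The last interval in Table 10.1-1, Week 12, is Days 64 to 91. Where several values share an interval, the last one counts: "If more than one observation falls within a particular trial day interval, then the last observation within that interval is used".

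The analyses that use these windows are in SAP 9.5 to 9.7. SAS, AIMS and BARS changes "for trial visits during the open-label treatment phase using the Safety Sample will be summarized by descriptive statistics". SAP 9.6 has similar wording for MMSE: "The mean changes from baseline in MMSE for trial visits during the open-label treatment phase will be summarized by descriptive statistics". SAP 9.7 adds: "Incidence of treatment emergent suicidal ideation, suicidal behavior will be summarized by treatment, and overall". None of the three sets a limit in days after the last dose. SAP 5.2 does not let baseline be carried forward in the LOCF dataset.

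**Baseline.** SAP 7.1 takes baseline from the parent trial's Week 12 visit and does not impute a missing value. Protocol 7.4.1 and the synopsis use the last measurement available before the first extension dose. SAP 3.1 and Figure 3.1-1 footnote b allow the parent ET visit if that trial is terminated, and SAP 7.3 refers to the last parent assessment visit.

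**The concern.** The body text and the closing paragraph cannot both be followed for an ET value obtained 8 or more days after the last dose. Footnote b does not settle the matter, because it names only efficacy while the convention also covers the safety scales.

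This matters most for MMSE and Sheehan-STS. Protocol Table 3.6-1 schedules each of them once after baseline, at Week 12 or ET. If that value is excluded, LOCF has nothing to replace it with, and the subject leaves the last-visit summaries and contributes no scheduled Sheehan-STS result to the suicidality incidence. Two programmers, each able to cite SAP 10.1, could report different denominators and counts.

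The baseline point is separate. Without a baseline value no change score can be derived, and the new-onset QTc categories in Table 9.4-1, which require absence at baseline, cannot be assigned.

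**Working it through.** **1. Reproduce the windows.** Targets are Days 7, 14, 42 and 84 (Table 10.1-1). Each upper bound is the midpoint to the next target, rounded down:

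- (7 + 14)/2 = 10.5, so 10
- (14 + 42)/2 = 28
- (42 + 84)/2 = 63
- last bound: 84 + 7 = 91

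These match the table's 10, 28, 63 and 91.

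**2. Who is caught by the 7-day rule.** A value is excluded when visit day minus last-dose day is 8 or more. For a Day 84 visit the latest such last dose is 84 - 8 = Day 76. Over the protocol's visit window of 2 days either side (Days 82 to 86), it runs from 82 - 8 = Day 74 to 86 - 8 = Day 78.

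**3. Apply each statement to a safety scale at an ET visit.**

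| Last dose | ET visit | Days after | Table interval | Body text | Footnote b | Closing paragraph |
|---|---|---|---|---|---|---|
| Day 20 | Day 30 | 10 | Week 6 | excluded | silent | mapped |
| Day 40 | Day 50 | 10 | Week 6 | excluded | silent | mapped |
| Day 60 | Day 70 | 10 | Week 12 | excluded | silent | mapped |
| Day 76 | Day 84 | 8 | Week 12 | excluded | silent | mapped |
| Day 83 | Day 91 | 8 | Week 12 | excluded | silent | mapped |

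If the Day 84 assessment is a scheduled Week 12 visit of a subject who has stopped IMP, the closing paragraph does not literally reach it. The open question is then whether the exclusion applies to all scales (body text) or to efficacy only (footnote b).

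**4. Scheduled values at stake per affected subject** (Protocol Table 3.6-1). MMSE has one after baseline, Sheehan-STS one, and the 30-day follow-up none. SAS, AIMS and BARS are also scheduled at Week 6, so LOCF can use that value if the subject reached Week 6 and was assessed. An earlier withdrawal has no such fallback.

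**5. The end of the last window.** Assume the last dose may fall on the day of an in-window Week 12 visit, so at latest on Day 86.

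- Last dose Day 82, 83 or 84: the 7-day limit is Day 89, 90 or 91, so there is no gap.
- Last dose Day 85: 85 + 7 = 92, so Day 92 has no window.
- Last dose Day 86: 86 + 7 = 93, so Days 92 and 93 have no window.

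Dosing beyond the visit window widens the gap (last dose Day 88: Days 92 to 95). An in-window Week 12 visit falls on Days 82 to 86, well inside 64 to 91, so only late or unscheduled values can land in the gap.

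**6. Baseline, by type of subject.**

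- Completer with a Week 12 value: SAP 7.1 and Protocol 7.4.1 agree, unless a test is repeated before the first dose.
- Completer with the Week 12 value missing but an earlier one available: the protocol gives a baseline, SAP 7.1 does not.
- Entrant from the parent ET visit (allowed by inclusion criterion 2): the protocol, SAP 3.1, Figure 3.1-1 footnote b and SAP 7.3 give a baseline; SAP 7.1, read literally, does not.

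**The case against.** The best defence is that the closing paragraph refers to the preceding algorithm, and that algorithm includes the 7-day exclusion. On this reading the windows catch off-schedule visits subject to one stated exception, and footnote b merely repeats it for efficacy. SAP 9.5 to 9.7 confine the summaries to the open-label treatment phase, which is compatible with an exclusion. This eases the conflict but does not remove it. It does not explain why footnote b is limited to efficacy, and the claim about all ET and unscheduled observations fails after Day 91 whether or not the exclusion applies.

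It is also fair to say that few subjects will be affected. Protocol 3.7.3.2 requires ET evaluations at the time of withdrawal. A late assessment is nevertheless foreseeable: Protocol 3.9 counts as completers those seen at Week 12 whatever doses they took, and Protocol 3.7.3.3 separates stopping IMP from withdrawing consent and asks for continued assessment where possible.

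On baseline, Protocol 7.6 states its definition only in general terms and lets it be specified otherwise, so SAP 7.1 does not breach that section. Protocol 7.4.1 and the synopsis carry no such exception, and SAP 7.1 still disagrees with other parts of the SAP. The parent-ET entrants may be none. The COVID-19 addendum requires the baseline visit in clinic, so missing Week 12 values should be few.

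A reader might go further in three ways that the documents do not support:

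- That scheduled Week 12 assessments are lost in the gap after Day 91. In-window visits end at Day 86.
- That exclusion criterion 2, by admitting subjects with a missing blood draw, leaves QTc without a baseline. A missing blood draw does not remove an ECG.
- That the SAP has dropped the parent-ET route altogether. SAP 3.2 no longer describes it, but SAP 3.1 and Figure 3.1-1 footnote b still do.

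**Conclusion.** The point holds, at low severity. SAP 10.1 does not give one treatment for safety-scale values 8 or more days after the last dose, and it promises a mapping that Table 10.1-1 cannot deliver after Day 91. For an affected subject the sole scheduled post-baseline MMSE and Sheehan-STS values are in or out according to the sentence followed. SAP 7.1 is, as a separate and minor matter, narrower than Protocol 7.4.1, the synopsis and the SAP's own SAP 3.1, Figure 3.1-1 footnote b and SAP 7.3.

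The number of subjects is not given and is probably small. A reader might want to express the effect as percentage points of suicidality incidence. The documents give no rollover number to divide by, so no such figure should be claimed.

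Nor does this reach the primary outcome. Adverse-event frequency and severity do not use these windows, and SAP 9.1 tabulates events up to 30 days after the last dose. The 10.1 convention lists scales only, so laboratory tests, vital signs and ECG are outside the window part of this point. The day arithmetic assumes that more than 7 days means a difference of at least 8, and that a dose may be taken on the day of the Week 12 visit.

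**What to change.** **SAP 10.1.** State one rule for values more than 7 days after the last dose, say explicitly whether it covers the safety scales, and make the body text, footnote b and the closing paragraph agree with it. End the Week 12 window at last dose + 7 days when that is later than Day 91; for an in-window last dose this reaches Day 93 at most. Keep the existing last-observation rule. If the exclusion is kept for the safety scales, flag the excluded values in a listing. Repeating the MMSE, Sheehan-STS and suicidality summaries with those values included is optional.

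**SAP 7.1.** Define baseline as the last measurement available before the first dose of IMP in Trial 331-201-00182, with the parent ET visit included, and align SAP 7.3.

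The cost is SAP wording and minor programming, plus one flagged listing if the exclusion stays. No new data are needed.
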